3.2 Rationale for Study Design

The purpose of this open label extension study is to evaluate the long-term safety of twice-monthly somavaratan subcutaneous dosing in adults with GHD.

There are currently no preventative treatments for GHD in children or adults. GH replacement therapy provides positive effects on body composition, lipid metabolism, bone metabolism, and quality of life in adults with GHD. Because the only currently available treatment is daily rhGH, compliance is an important barrier to these benefits; patients either missing doses or opting to forego treatment altogether due to the burden of daily injections.^{29,31} Somavaratan is being developed for twice-monthly dosing in GHD adults to provide an alternative to daily dosing that may avoid these compliance and adherence problems and attendant loss of treatment effect.

3.3 Dose Selection

The current standard of care for adult subjects with GHD who are being treated with daily rhGH is to initiate therapy at a low dose of rhGH (e.g., 2 µg/kg/day) and then titrate the dose up or down based on IGF-I measurements (the primary PD parameter) and the presence or absence of adverse events. Each subject may have different IGF-I and safety responses to rhGH treatment, especially with regards to potential adverse events such as edema. Consequently, somavaratan dosing will also be titrated to an individual's IGF-I SDS response with the aim of safely achieving normalization of IGF-I SDS.

The doses subjects receive in this study will be based on the evaluation of data obtained in the Phase 2 study and on oral estrogen use, because women using oral estrogens are less sensitive to rhGH.^{28,29} Section 4 describes somavaratan treatment in detail.

3.4 Study Duration and Dates

This study is a long-term evaluation of somavaratan administered twice-monthly. Subjects may continue on somavaratan treatment until the product is commercially available in their country or until the study is discontinued by the sponsor.

3.5 Safety Review and Stopping Rules

Subjects will be monitored for safety throughout their participation in the study. Safety will be monitored by physical examination, inspection of injection sites, vital signs, clinical laboratory determinations, PK/PD assessments, and immunogenicity assessments. AEs will be graded using the Common Terminology Criteria for Adverse Events (CTCAE v 4.0). AEs will be coded using the MedDRA dictionary and CMs using the WHO Drug dictionary.

An external data and safety monitoring board (DSMB) will monitor and protect the safety of the study subjects throughout the study duration. DSMB meetings will occur twice yearly (approximately every 6 months).

In accordance with the DSMB Charter, summaries of data will be prepared by the project statistician. The data for review will be outlined in the DSMB charter and will be agreed to in advance by the DSMB members.

The DSMB may recommend modifications of the protocol to enhance subject safety and to recommend early termination of the study if there is strong evidence that somavaratan poses a safety concern to subjects in the study.

3.5.1 Stopping Rules

The Stopping Criteria include:

1. The Principal Investigator (PI) and/or Medical Monitor conclude it is unsafe or not in the subject's best interest to continue.
2. IGF-I SDS \geq 3.0 SDS on two consecutive Day 8 time points despite dose adjustments
3. IGF-I SDS \geq 2.0 SDS on two consecutive Day 8 time points despite dose adjustments and accompanied by clinically meaningful drug-related AEs, as determined by the Investigator and the Medical Monitor.

Subjects meeting individual stopping criteria will be withdrawn from the study.

The Stopping Criteria for a dosing cohort or the study include the determination that the dosing cohort or the study is unsafe to continue.

STUDY POPULATION SELECTION

3.6 Study Population

The study population will consist of adults age 18-75 years (inclusive) who have well-established growth hormone deficiency (GHD) according to the Endocrine Society guidelines.¹⁴ A total of up to 250 subjects may be enrolled. Eligible subjects will have completed a Versartis adult GHD study or will be included as new subjects who are either rhGH treatment naïve or transitioned from daily rhGH therapy to twice-monthly somavaratan. New subjects receiving daily rhGH treatment must discontinue daily rhGH use for a minimum of 14 days prior to somavaratan dosing.

3.7 Inclusion Criteria:

Eligible subjects must meet all inclusion criteria.

1. Female or male subjects, between 18 and 75 years (inclusive) of age, with the diagnosis of AGHD.
2. Eligible subjects may be naïve to somavaratan or have previously received somavaratan in the setting of a prior Versartis study.
 - Subjects naïve to somavaratan must have a documented medical history of GHD during adulthood according to the Endocrine Society guidelines¹⁴ (confirmatory testing should be done to document persistence of childhood onset GHD into adulthood if necessary)
 - Subjects who have previously received somavaratan in the setting of a prior Versartis study can be included in this study if they have not met a stopping criteria in the corresponding study and somavaratan was well tolerated as judged by the Investigator and the Medical Monitor
3. Naïve to somavaratan subjects must have an IGF-I SDS value ≤ 0 at Screening (inclusive).
4. All subjects must agree to the contraceptive requirements outlined in Appendix 3, if applicable.
5. Female subjects of childbearing potential must have a negative pregnancy test at Screening and on Day 1.
6. Naïve subjects who are taking any other hormone replacement therapy must have been on a stable course of treatment for at least 3 months prior to Screening (routine dose adjustments are acceptable). Subjects transitioning from other Versartis adult GHD studies and who are receiving other hormone replacement therapy may have experienced dose adjustments or initiation of treatment during their previous study and may continue treatment per standard clinical practice.

7. Naïve subjects currently receiving daily recombinant human growth hormone (rhGH) injections for treatment of GHD, must agree to stop taking prescribed daily rhGH therapy for the washout period of ≥ 14 days.
8. Underlying disorders responsible for the subject's GHD must have been clinically stable for at least 6 months prior to Screening.
9. Subjects must provide written informed consent.
10. Subjects must have a BMI (kg/m²) between 18.0 and 40.0 (inclusive).

3.8 Exclusion Criteria:

Subjects with the following conditions/criteria will be excluded.

1. Subjects with untreated adrenal insufficiency or unknown adrenal function. Prior Versartis study subjects will have been previously screened, however new subjects will require documentation of adrenal function via adrenal stimulation test prior to treatment. New subjects must have had an adrenal stimulation test within 3 months prior to treatment with somavaratan. Adrenal stimulation tests (as well as repeat/follow-up testing in at-risk patients) will be performed per institutional protocol.
2. Subjects with recently diagnosed thyroid dysfunction who have not started treatment or have not been stable on therapy for at least 3 months.
3. Subjects currently taking anti-inflammatory dose of glucocorticoids that could potentially compromise safety or efficacy assessments.
4. Subjects currently receiving any GHRH or IGF-I product.
5. Subjects with current significant cardiovascular disease, heart insufficiency of NYHA class > 2 .
6. Subjects with significant comorbidities thought to increase risk of receiving growth hormone treatment or confound assessment of study outcomes (e.g. hepatic or inflammatory disorders that may affect GH-mediated hepatic IGF-I production or renal disorders that may alter somavaratan PK).
7. Subjects with a documented history of diabetes mellitus or inadequate glucose control as defined by a historical or Screening value of: FPG > 126 mg/dL (7 mM), or HbA1c $\geq 6.5\%$.
8. Subjects with current papilledema.
9. Subjects with current drug or alcohol abuse.
10. Subjects with a documented history of HIV, current HBV or HCV infection (testing not required).
11. Subjects with a history of malignancy in adulthood (subjects with a history of childhood malignancy that were subsequently treated with rhGH in childhood and remain GHD in adulthood may be enrolled).

12. Women who are pregnant or breastfeeding.
13. Subjects treated with an investigational drug other than somavaratan within 30 days prior to Screening.
14. Subjects with a significant abnormality in Screening test results as interpreted by the Investigator and the Medical Monitor.
15. Impossibility of or unwillingness to participate in all trial activities.

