2 STUDY OBJECTIVES

2.1 Primary Objective

The primary objective of this study is:

- To evaluate the safety of somavaratan during long-term treatment in adults with GHD

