8.2 Analysis Populations

8.2.1 *Safety Population*

The safety population will consist of all subjects who receive any amount of study drug.

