8.5 Safety

Safety analyses will be conducted on the safety population and will be summarized by cohort. Safety variables include AEs, clinical laboratory values, vital signs, and physical examination results.

AEs will be coded using MedDRA and will be summarized using the coded terms. Summaries of all treatment emergent adverse events (TEAEs), serious adverse events (SAEs) and Suspected, Unexpected Serious Adverse Reactions (SUSARs) will be presented. The incidence of CTCAE V.4.0 Grade 3 or 4 adverse events will be classified according to severity and relationship to study drug.

Observed and change from Baseline values for laboratory safety panels and vital signs will be summarized using descriptive statistics. Laboratory results will also be summarized and presented as shifts from Baseline.

No formal inferential analyses will be conducted for safety variables.

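### Safety is tabulated only by oral-estrogen cohort, so each column pools about 40 somavaratan-naive subjects with rollovers already selected for tolerating the drug, and the pooled incidence describes neither group

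*Combined protocol and SAP*

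**What the plan says.** - **Objective (2.1).** The primary objective is "To evaluate the safety of somavaratan during long-term treatment in adults with GHD".
- **Who enters (3.6, and 3.7 criterion 2).** "Eligible subjects will have completed a Versartis adult GHD study or will be included as new subjects". Those who have already had somavaratan must also satisfy the condition that "they have not met a stopping criteria in the corresponding study and somavaratan was well tolerated as judged by the Investigator" and the Medical Monitor. Section 3.1 expects about 40 somavaratan-naive subjects and sets a cap of 250 in all.
- **Glucose (3.8, criterion 7).** The exclusion covers "Subjects with a documented history of diabetes mellitus or inadequate glucose control as defined by a historical or Screening value of" FPG above 126 mg/dL or HbA1c of at least 6.5%. It is written for every subject and has no rollover exception.
- **Analysis set (8.2.1).** "The safety population will consist of all subjects who receive any amount of study drug".
- **Tables (8.1, 8.5).** All summaries are by cohort, and "Safety analyses will be conducted on the safety population and will be summarized by cohort". Section 3.1 and Table 1 define cohort by oral-estrogen use. The only other adverse event subgroup named, in the synopsis, is anti-drug antibody status.
- **Time origin (5.7.2, 8.1).** Adverse event recording starts at consent. Baseline is the last value before the first dose in 15VR8.

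**The concern.** Rollovers are selected on something close to the primary outcome: they have already received somavaratan and been judged to tolerate it. New subjects have not. In the planned tables the two groups share a column.

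Two mechanisms can separate their event rates. Subjects who did badly on somavaratan in the parent study do not enter. Rollovers who had an early event and continued had it before 15VR8 recording began. Their laboratory shifts also start from an on-treatment Baseline.

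The study plans no hypothesis tests, so the incidence tables are its primary result. If the groups differ in either direction, a pooled percentage cannot be read as the risk on starting somavaratan or as the risk on continuing it. The naive subjects are the only group followed in this study from their first somavaratan dose, and they may be a small part of each column.

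**Working it through.** **What can be reproduced.** The cap of 250 has no derivation, and the documents give no adverse event rate by prior exposure, so there is no planned incidence to reproduce. The Phase 2 IGF-I percentages in the amendment rationale do check: 19/36 = 52.8% (stated 53%), 14/36 = 38.9% (39%), 16/29 = 55.2% (55%) and 7/29 = 24.1% (24%).

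**Do the columns mix the groups?** The titration table applies to all subjects and is indexed by cohort, so rollovers carry a cohort as new subjects do. Everyone dosed is in the safety population. No planned summary is by prior exposure. On a plain reading, they mix.

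**Rollover share, w.**
- At the cap: (250 - 40)/250 = 210/250 = 84%. This is a ceiling, not a forecast.
- Illustration with the 36 Phase 2 subjects who had Day 8 data after the first dose: 36/(36 + 40) = 47%.
- Illustration with the 29 who had received five doses: 29/(29 + 40) = 42%.

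**Effect of pooling.** Let p be the naive incidence and RR the rollover risk divided by the naive risk. RR is an assumption.

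Pooled incidence = (1 - w) × p + w × RR × p, so relative change = w × (RR - 1).

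| RR | w = 47% | w = 84% |
|---|---|---|
| 0.5 | -24% | -42% |
| 0.75 | -12% | -21% |
| 1.0 | 0 | 0 |
| 1.25 | +12% | +21% |

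With p = 20% and w = 84%, for example, the pooled figure is 11.6% at RR 0.5, 15.8% at 0.75, 20% at 1.0 and 24.2% at 1.25.

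**What the entry filter alone would have to do.** Suppose an event has risk 30%, and a fraction f of parent-study subjects is kept out because of it. Then RR = (0.30 - f)/[0.30 × (1 - f)].
- f = 2%: RR = 0.28/0.294 = 0.952. The understatement is 2.3% (w = 47%) to 4.0% (w = 84%).
- f = 10%: RR = 0.20/0.27 = 0.741. The understatement is 12% to 22%.
- RR = 0.5 needs f = 0.15/0.85 = 17.6%, which is 59% of those with the event.

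Both 30% and f are assumptions. An RR near 0.5 from the filter alone would need heavy exclusion. Events that fall in the parent study are a second route to a low RR, and the documents give no data to size it.

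**Precision of a separate naive column.** With zero events, the one-sided 95% upper bound is 1 - 0.05^(1/n): 7.2% for n = 40 and 1.2% for n = 250. At an incidence of 20%, the 95% half-width 1.96 × √(0.2 × 0.8/n) is 12.4 points for n = 40 and 5.0 points for n = 250.

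**The case against.** The strongest reply is that this is an extension study whose objective concerns long-term treatment. People who continue are a proper target group, every extension is selected in this way, and first-exposure incidence belongs mainly to the parent studies. That stands. Rollover rates are valid for continuing patients. The fault lies in merging the groups and then reading the result as the risk for someone starting the drug.

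A reader might go further and infer that incidence is understated, always in one direction. The documents do not support that. RR is not given, and some facts could push it above 1: 16 of 29 Phase 2 subjects with five doses had Day 8 IGF-I above 2.0 SDS, and the amendment says about half of rollovers still have high Day 8 values. Rollovers also enter at no less than the 20 mg at which Cohort 1 starts.

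Three other stronger readings also fail:
- The glucose exclusion is not in itself a survivor filter. It binds new subjects too, and adds to rollover selection only where the value arose on somavaratan. No such case is documented, and the related events listed in 5.7.5 include no glucose event.
- The difference between 36 and 29 Phase 2 subjects is not attrition, because that study was still running.
- The naive group is not wholly unselected. It may include people on daily rhGH who already tolerate growth hormone.

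Finally, 8.1 calls itself a brief summary and defers detail to a SAP. No separate SAP text is in the material supplied, so the split may be planned there. The protocol does not require it.

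**Conclusion.** The point holds as one about what the tables describe. As written, the primary safety columns mix continuers selected for tolerability with about 40 first-exposure subjects, and no planned table separates them. Understatement of early-onset and tolerability events in new starters is the likely direction, but it is not established. Its size depends on an assumed RR and on a share known only as a ceiling: -24% to -42% at RR 0.5, about half that at 0.75, nil at 1, and reversed above 1.

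A reader might infer that the pooled column should be barred from the primary conclusion. That does not follow: the pooled column holds most of the long-term exposure, which is what the objective asks about. The case for change is that the split is cheap, and the protocol already distinguishes new from rollover subjects for ECGs, the Screening PD sample and the Month 1 antibody sample.

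**What to change.** Leave eligibility and visits as they are and amend 8.5, with matching SAP text:

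1. Keep the pooled cohort columns for long-term safety.
2. Within each cohort and overall, add separate columns for somavaratan-naive and rollover subjects. Cover TEAEs, SAEs, Grade 3 or higher events, adverse events leading to withdrawal, and glucose-metabolism shifts.
3. Base any statement about incidence on starting somavaratan on the naive column.
4. In disposition, report how many parent-study subjects did not enter 15VR8 and why: not completed, stopping criterion met, not tolerated, glucose or other exclusion, or choice.

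The cost is extra columns and a count from parent-study records that the sponsor should hold. The naive column will be imprecise, as the bounds above show, and should be reported with that caution.

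A table counting rollover events from the first parent-study dose is optional. It would bring in events from the once-monthly, weight-based regimen that this version replaced, and is better placed in an integrated safety summary.

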3.9 Subject Withdrawals and Replacements

Consent may be withdrawn at any time for any reason by a subject without prejudice to future treatment. The Investigator or Medical Monitor may withdraw a subject if it is judged to be in the best interest of the subject or if it is clear the subject cannot comply with the protocol.

Subjects that develop a new significant medical condition at any point during the study may be withdrawn. Subject numbers will not be re-assigned. Subjects will not be replaced.

4 STUDY TREATMENT(S)

4.1 Description of Treatment(s)

4.1.1 Somavaratan Treatment

Somavaratan will be provided either in a vial and syringe configuration or as an autoinjector device (when available) and administered as subcutaneous injection(s) in the thigh, abdomen, upper arm or buttocks. Injection sites shall be rotated. Study drug may be administered by trained subjects/caregivers, or a health care professional.

Somavaratan is formulated at a nominal concentration of 100 mg/mL in 20 mM histidine, 154 mM sodium chloride, pH 5.5. Somavaratan is a colorless, clear liquid, free from visible particles. See Section 4.2 for starting dosages.

4.2 Treatments Administered

All subjects will receive somavaratan twice-monthly.

- Subjects receiving somavaratan once monthly in a prior Versartis adult GHD study or in this study, irrespective of the cohort assignment and whether they have achieved maintenance dosing, will transition to receive treatment at half of their current dose (rounded down to the nearest even number, minimum dose of 20 mg).
- New subjects naïve to somavaratan will be assigned to one of two treatment cohorts (Table 1) with different starting doses based on the subject's use of oral estrogens. The initial dose will be a fixed dose.

All subjects will have Day 8 IGF-I SDS evaluated each month with subsequent dose adjustments made per the Dose Titration Plan (Table 2).

Table 1 Study Drug Starting Dose Information

Subject Cohort Assignment	Fixed Starting Study Dose	Frequency of Administration
Cohort 1: Adults with GHD irrespective of age and gender	20 mg	Twice-Monthly ¹
Cohort 2: Women receiving oral estrogens	40 mg	Twice-Monthly ¹

1: Allowable dosing window is every 15 days ± 2 days

Table 2 Dose Titration Plan

Downward Dose Titration		
IGF-I at Day 8	Cohort 1	Cohort 2
0 to 2.0 SDS	No change in dosing	No change in dosing
2.01 to 3.0 SDS	4 mg dose decrement	4 mg dose decrement
Greater than 3.0 SDS	10 mg dose decrement	10 mg dose decrement
Upward Dose Titration¹		
IGF-I at Day 8	Cohort 1	Cohort 2
-1.0 to 0 SDS	4 mg dose increment	10 mg dose increment
-1.0 to -2.0 SDS	10 mg dose increment	20 mg dose increment
Less than -2.0 SDS	20 mg dose increment	40 mg dose increment

1: Maximum allowable dose is 250.0 mg

The starting doses and Dose Titration Plan (Tables 1 and 2) may be altered by the Sponsor based on continued evaluation of the Phase 2 data and/or data gathered during this study. Adjustments may be implemented to alleviate safety concerns or optimize normalization of IGF-I SDS responses. The Investigator and Medical Monitor may agree to temporarily alter or suspend a subject's dose during illness or injury.

If a subject on maintenance dose has an IGF-I value outside the target range, further dose adjustments will be considered on an individual basis by the Investigator or Medical Monitor with the objective to achieve and maintain IGF-I SDS at Day 8 within target range (IGF-I SDS between 0 - 2.0)

